**D.13. Potential problems and alternative strategies.**

**D.13.1. Why we are not examining individuals with treated hypertension.** The focus of this application is on the diagnosis of hypertension. Many guidelines and scientific statements recommend ABPM for confirming the diagnosis of hypertension. Although ABPM can also be used to monitor on-treatment BP for people with hypertension and who are taking antihypertensive medication, this is a less common recommendation.

**D.13.2. Why is ABPM and not HBPM the reference standard for awake BP.** We have chosen to use ABPM rather than HBPM to assess awake BP because it is widely considered the reference standard for out-of-clinic BP assessment and confirming hypertension status. Further, conducting HBPM to assess awake BP was not practical for the proposed study because it requires up to 7 days of measurements, which will confound the ability to assess the tolerability of the HBPM device for assessing sleep BP, based on a single night.

**D.13.3. Why we are not comparing BP dipping and morning surge assessed using HBPM versus ABPM.** We are not studying BP dipping and morning surge because the prognostic value of these phenotypes is unclear. Some studies have reported associations of these phenotypes with outcomes while others have not. Additionally, the reproducibility of these phenotypes is poor. Finally, these phenotypes are not widely used in clinical practice particularly for the diagnosis of hypertension.

**D.13.4. Hypotheses in Aim 1 but not Aim 2 (or vice versa) are confirmed.** If the hypotheses in Aims 1 and 2 are confirmed, there will be a unified approach to accurately diagnose hypertension without ABPM (i.e., conduct unattended BP for detecting awake hypertension and HBPM for detecting sleep hypertension). If the hypotheses for only one aim are confirmed, then our study would inform when unattended BP or sleep HBPM should be used. For example, if Aim 1 but not Aim 2 is confirmed, unattended BP measured in the clinic can be used to assess awake hypertension but an abbreviated form of ABPM (conducted during the sleep period) is needed. If Aim 2 but not Aim 1 is confirmed, ABPM can be used during the awake period to exclude awake hypertension while sleep HBPM, if better tolerated, can be used for assessing sleep hypertension. In both scenarios, the burden of performing ABPM during a 24-hour period is reduced.

**D.14. Translation into practice.** Upon completion of the study, we will conduct a stakeholders meeting with clinical leaders in the field of hypertension to develop a statement on the use of unattended BP and sleep HBPM assessment in clinical practice. This meeting will include committee members from the AHA's Scientific Statement on BP measurement, which [name] and [name] co-chair. [name] is director of the Lister Hill Center for Health Policy at UAB and will use center funds for this meeting.

**D.15. Reproducibility and transparency.** We will post the aims, methods, and original analytical plan prior to data collection on the Open Science Framework website, which is hosted by the recently founded Center for Open Science (funded in part by the NIH and the National Science Foundation; <https://osf.io>), and is open to the public to view. Once the proposed study has been completed and before data analyses are initiated, we will post the code for derivation of study variables and the final sample size (with a flow diagram on how the final sample was derived). For each abstract and manuscript, all coding will be carefully labeled and linked to the final versions of each document. None of the posted documents will contain participant identifiers.

**D.16. Consideration of sex and other biological variables.** We will make every effort to recruit equal numbers of men and women. As noted above, we will conduct exploratory analyses stratifying by age group, sex, and race/ethnicity (white, African American, and Hispanic; a minimum of 160 each).

**D.17. Summary.** In clinical practice, BP is typically measured in the clinic by a technician/healthcare provider. This approach often leads to an inaccurate diagnosis of hypertension. Several guidelines and scientific statements recommend the use of ABPM, which measures BP during the awake and sleep periods, for confirming the diagnosis of hypertension. However, ABPM is not being done in clinical practice due to several barriers that limit its widespread use. Therefore, new and innovative approaches for diagnosing hypertension without conducting ABPM are needed. Some data suggest that BP measured unattended versus attended is closer to awake BP on ABPM. However, these data were derived from uncontrolled, non-randomized studies of select patients and were considered sufficiently low quality in the Canadian Guidelines to warrant a Grade D level of evidence. Another approach is to use a new HBPM device that has been developed to assess sleep BP. Using a randomized controlled trial design, the study will rigorously test these two non-ABPM approaches for determining awake and sleep BP. The novel approaches being tested can be adopted in clinical practice and may become the standard-of-care for diagnosing hypertension if our hypotheses are confirmed.

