### **Aims and hypotheses**

**Primary Aim 1:** To examine whether measuring unattended clinic BP with an automated device will provide a more accurate estimate of awake BP on ABPM than measuring attended clinic BP with an automated device.

**Hypothesis 1a:** The absolute difference with awake BP will be smaller for unattended vs. attended clinic BP.

**Hypothesis 1b:** The agreement between hypertension status using BP measured in the clinic and on ABPM while awake will be higher when clinic BP is measured unattended vs. attended. Also, the prevalence of both white coat and masked hypertension will be lower when measuring unattended clinic BP.

**Primary Aim 2:** To examine whether a new HBPM device provides an accurate approach for measuring sleep BP.

**Hypothesis 2a:** Sleep BP on HBPM will provide an accurate estimate of sleep BP on ABPM.

**Hypothesis 2b:** HBPM will be better tolerated (e.g., less awakening during sleep, pain, bruising) than ABPM.

**Primary Aim 3:** To compare the associations of unattended versus attending clinic BP, unattended clinic BP versus awake BP on ABPM, and sleep BP on HBPM versus ABPM with two markers of end-organ damage, left ventricular mass index (LVMI) and urinary albumin-to-creatinine ratio (ACR).

**Hypothesis 3a:** The association with end-organ damage will be stronger for unattended vs. attended clinic BP.

**Hypothesis 3b:** The association with end-organ damage will be similar for unattended clinic BP and awake BP.

**Hypothesis 3c:** The association with end-organ damage will be similar for sleep BP by HBPM and ABPM.

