Nocturnal hypertension, typically defined by mean sleep SBP/DBP  $\geq 120/70$  mm Hg, affects ~1 in 3 adults and is associated with increased CVD risk, independent of clinic and awake BP. Therefore, a comprehensive approach to diagnosing hypertension requires measuring sleep BP in addition to awake BP. Ambulatory BP monitoring (ABPM) is a procedure wherein people have their BP measured automatically every 15 to 30 minutes, typically for 24 hours, outside of the clinic setting. ABPM is widely considered to be the reference standard for diagnosing hypertension. However, ABPM is not available in most clinics in the US and is poorly tolerated by patients. Recently, home BP monitoring (HBPM) devices have been developed that measure BP during sleep. These devices may be better tolerated than ABPM as they are only worn at night and fewer BP measurements are obtained. **We propose to compare novel non-ABPM approaches for measuring BP and diagnosing hypertension with ABPM, the reference standard.** The study aims are:

**Aim 1. Test whether measuring unattended clinic BP with an automated device will provide a more accurate estimate of awake BP on ABPM than measuring attended clinic BP with an automated device.**

*Hypothesis 1a: The absolute difference with awake BP will be smaller for unattended vs. attended clinic BP.*

*Hypothesis 1b: The agreement between hypertension status using BP measured in the clinic and on ABPM while awake will be higher when clinic BP is measured unattended versus attended. Also, the prevalence of both white coat and masked hypertension will be lower when measuring unattended versus attended clinic BP.*

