#### D.12.1.1. Sample size considerations for hypothesis 1a.

**Figure 4** shows the minimal detectable difference in differences with awake ABPM comparing unattended vs attended clinic BP. With 600 participants we can detect that the absolute difference with awake ABPM is 1.5 and 1.2 mm Hg smaller for unattended vs attended clinic BP assuming a correlation of 0.5 and 0.7, respectively between clinic BP and awake BP on ABPM. In a sub-group of 160 participants (e.g., African Americans), we can detect that the absolute difference with awake ABPM is 3.1 and 2.4 mm Hg smaller for unattended vs. attended clinic BP.

Smaller absolute differences can be detected if the correlation between attended and awake BP is higher.

**D.12.1.2. Sample size considerations for hypothesis 1b.** If 85% of participants have the same concordance/discordance status for both comparisons (i.e., attended clinic hypertension versus awake hypertension and unattended clinic hypertension versus awake hypertension), enrollment of 600 participants will provide 80% statistical power to detect a difference of 5% in the two overall agreements (e.g., 70% vs. 75%). If the expected agreement is 50%, we will have an 80% statistical power to detect a difference between Kappa statistics of 0.4 and 0.5 using a two-sided alpha level of 0.05. With 600 participants and a phenotype prevalence of 15%, we can detect a difference in the prevalence of 4% when clinic BP is measured unattended versus attended. In a sub-group of 160 participants, we can detect a difference of 8%. Based on these estimates, we chose to enroll 630 participants in the proposed study (n=600 with complete data).

#### D.12.2. Aim 2

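### Confirming Aim 1 would show only that unattended clinic BP beats attended BP, yet D.13.4 concludes that it can stand in for awake ABPM, with no absolute accuracy criterion

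*Combined protocol and SAP*

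**What the plan says.** D.13.4 sets out what follows from each pattern of results. If both aims succeed, "there will be a unified approach to accurately diagnose hypertension without ABPM". If only the first succeeds, "if Aim 1 but not Aim 2 is confirmed, unattended BP measured in the clinic can be used to assess awake hypertension". In that case monitoring overnight is retained: "but an abbreviated form of ABPM (conducted during the sleep period) is needed". The statement for both aims is conditional on the hypotheses in the plural: "If the hypotheses in Aims 1 and 2 are confirmed, there will be a unified approach to accurately diagnose hypertension without ABPM".

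The Aim 1 hypotheses are comparative throughout. Hypothesis 1a reads "The absolute difference with awake BP will be smaller for unattended vs. attended clinic BP". Under Hypothesis 1b, agreement with awake hypertension "will be higher when clinic BP is measured unattended versus attended", and "the prevalence of both white coat and masked hypertension will be lower when measuring unattended versus attended clinic BP".

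D.11.3 plans intraclass correlations and Bland-Altman plots of each clinic method against awake BP. D.11.4.1 tests each clinic-minus-awake difference against zero, and then tests whether the difference in differences is below zero. D.11.4.2 plans overall agreement and kappa of each clinic method with awake hypertension. The Analysis Plan (Statistical analysis, item 4) instead produces Tables 4 to 6, each of which crosses a phenotype defined with attended BP against the same phenotype defined with unattended BP.

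**The concern.** A method can be better than a weak comparator and still be too inaccurate to replace the reference standard. D.13.4 moves from the first statement to the second without a test that links them. Aim 2 is handled differently: D.12.2.1 frames it as equivalence of HBPM and ABPM and gives the mean differences that can be excluded (2.1 mm Hg SBP, 1.4 mm Hg DBP). Aim 1 has no counterpart.

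The planned analyses against awake BP do not close the gap. A non-significant difference from zero does not demonstrate equivalence, and a mean difference near zero says nothing about error in the individual patient. The correlations, plots and kappas come with no value that Aim 1 must reach.

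The conclusion at stake is the study's main message for practice. The summary in D.17 says that the approaches may become standard of care if the hypotheses are confirmed.

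**Working it through.** **1. Reproduce the plan's own agreement figure.** Table 4 has cells 25, 1, 14 and 529 (N=569).

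- Observed agreement = (25 + 529)/569 = 0.9736.
- Chance agreement = (26×39 + 543×530)/569² = 0.8920.
- Kappa = (0.9736 − 0.8920)/(1 − 0.8920) = 0.76, as printed.

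The table is titled as agreement between hypertension on ABPM and clinic BP. Its rows are ABPM plus attended hypertension and its columns ABPM plus unattended hypertension. The 0.76 therefore measures how well the two clinic methods match each other, not how well either matches ABPM.

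**2. Rebuild the comparison with awake hypertension.** Counts come from the margins of Tables 4, 5 and 6.

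- Awake hypertension: 39 + 18 = 57 (also 26 + 31 = 57). 57/569 = 10.0%, as in Table 3.
- Unattended hypertension: 39 + 41 = 80. 80/569 = 14.1%, as in Table 3.
- Attended hypertension: 26 + 15 = 41. 41/569 = 7.2%, as in Table 3.
- No awake hypertension: 569 − 57 = 512. True negatives: 512 − 41 = 471 unattended, 512 − 15 = 497 attended.

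| Against awake hypertension | Unattended | Attended |
|---|---|---|
| Sensitivity | 39/57 = 68% | 26/57 = 46% |
| Specificity | 471/512 = 92% | 497/512 = 97% |
| PPV | 39/80 = 49% | 26/41 = 63% |
| NPV | 471/489 = 96% | 497/528 = 94% |
| Overall agreement | 510/569 = 89.6% | 523/569 = 91.9% |
| Kappa | 0.51 | 0.49 |

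Kappa, unattended: chance agreement = (80×57 + 489×512)/569² = 0.787, so (0.896 − 0.787)/(1 − 0.787) = 0.51. Kappa, attended: chance agreement = (41×57 + 528×512)/569² = 0.842, so (0.919 − 0.842)/(1 − 0.842) = 0.49.

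Wilson 95% intervals for unattended BP are 56% to 79% for sensitivity and 38% to 60% for PPV. The two methods use different cut-points (135/85 unattended, 140/90 attended), so part of the contrast between columns reflects the threshold.

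**3. Limits of agreement for SBP.** Table 2 gives ABPM versus unattended as −0.004 (−0.64, 0.64). Treating the interval as that of a paired mean:

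- SD = 0.64/1.964 × √569 = 7.8 mm Hg.
- Limits = −0.004 ± 1.96 × 7.77 = about −15 to +15 mm Hg.

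**4. How the parts of Aim 1 fall in the reported tables.**

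| Part | Unattended | Attended | Favours |
|---|---|---|---|
| Mean SBP difference, ABPM minus clinic | −0.004 | −0.69 | Unattended |
| Mean DBP difference, ABPM minus clinic | 2.03 | 1.55 | Attended |
| Overall agreement | 89.6% | 91.9% | Attended |
| White coat prevalence | 7.2% | 2.6% | Attended |
| Masked prevalence | 3.2% | 5.5% | Unattended |

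**5. The sample-size statement is also relative.** D.12.1.1 says "With 600 participants we can detect that the absolute difference with awake ABPM is 1.5 and 1.2 mm Hg smaller". The SD is not given, so the figures cannot be reproduced exactly. With (1.96 + 0.84) × SD × √(2(1 − r))/√600, and r also assumed between the two clinic methods, an SD of 13 gives 1.49 at r=0.5 and an SD of 13.5 gives 1.20 at r=0.7. The figures are plausible, but they describe a gain over attended BP and not closeness to ABPM.

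**The case against.** Four points can be made for the plan.

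- **D.13.4 is not a formal decision rule.** It sits under potential problems and alternative strategies, and the sentence about Aim 1 alone is introduced as an example. The Analysis Plan contains no substitution rule. This lowers the weight of the point, but the claim is still stated without qualification and D.17 repeats its substance.
- **Absolute analyses are planned.** D.11.3 to D.11.4.2 do compare unattended BP with awake BP, and Hypothesis 3b compares the two through end-organ damage. This stands, and it narrows the gap to the missing pass mark and to the absence of these comparisons from the Analysis Plan's tables.
- **Hypothesis 1b bears on accuracy.** White coat and masked prevalence are the false-positive and false-negative proportions against ABPM. Requiring both to be lower is a real hurdle, but lower than attended is still not low enough in any stated sense.
- **Some ABPM stays.** If only Aim 1 is confirmed, sleep-period ABPM is retained, so only awake monitoring would be replaced.

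A reader might infer that a trivial SBP gain, below 1 mm Hg, could by itself license dropping ABPM. The documents do not support that. D.13.4 speaks of the hypotheses together, and in the reported tables a 0.69 mm Hg SBP difference (P<.0001) came with higher white coat prevalence and lower overall agreement, so 1b is not met.

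A reader might also back-calculate from Table 2 that about 0.4 mm Hg is detectable with 600 participants. That figure rests on the SD of signed attended-minus-unattended differences. Hypothesis 1a concerns absolute differences from awake BP, whose person-level SD cannot be recovered. The planned primary analysis uses the first three readings at each visit, whereas Table 2 appears to use six-reading means: 179.8 and 47.2 cannot be averages of three whole-number readings. The plan's own figures are 1.2 to 1.5 mm Hg.

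**Conclusion.** The point holds as a gap between hypothesis and conclusion. Every part of Aim 1 is relative to attended BP, so even complete confirmation would not show that unattended BP can replace awake ABPM. No accuracy criterion against awake ABPM exists anywhere in the plan.

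The gap matters in the reported data. Unattended BP misses 18 of 57 awake hypertensives, and 41 of its 80 positives are not hypertensive on awake ABPM. Individual SBP differences span about ±15 mm Hg around a mean of almost zero. The printed kappa of 0.76 could be mistaken for accuracy against ABPM, where the rebuilt value is about 0.51.

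The 2×2 results are exact from the printed counts. The limits of agreement assume that the Table 2 interval behaves like a paired-mean interval and that differences are roughly normal. No sample size, data collection or planned test is shown to be invalid. What needs correction is the permitted conclusion and the reporting that supports it.

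Because the parts of Aim 1 split, a reader might be tempted to define confirmation on SBP alone. The plan analyses SBP and DBP separately and defines hypertension by either. With results visible, choosing the measure that favours unattended BP would be outcome-driven.

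**What to change.** 1. Reword D.13.4 so that confirmation of Aim 1 supports only the statement that unattended is preferable to attended clinic BP. State that this requires all parts of 1a and 1b, for both SBP and DBP, as the plural wording implies.
2. Add one table to the Analysis Plan giving sensitivity, specificity, predictive values, overall agreement and kappa of each clinic method against awake hypertension, with 95% confidence intervals. Report the limits of agreement from the Bland-Altman analysis already planned in D.11.3 beside it.
3. Make any statement about substituting for awake ABPM depend on an absolute accuracy criterion set by the investigators. Label that criterion post hoc, because results already stand in the document.

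The cost is a wording change and one table from data already collected. The downside is a narrower permitted claim.

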## **E. HUMAN SUBJECTS**

### **E.1. Protection of Human Subjects**

#### **E.1.1. Risks to the Subjects**

**Human subjects involvement and characteristics:** The proposed study will include 630 participants from Birmingham, AL (N=315) and New York, NY (N=315). Study participants will be recruited between 2019 and 2022. Participants will be  $\geq 21$  years of age. No participants will have hypertension and no participants will have cardiovascular disease. We plan for the overall sample to include an equal percentage of men (50%) and women (50%) and at least 25% of the population will be white, 25% African Americans and 25% Hispanic.

**Sources of materials:** Research material for the study includes self-report and physiological data, both of which are collected specifically for the purpose of the study. The physiological measurements consist of the assessment of orthostatic hypotension (from supine and standing blood pressure measurements), noninvasive measurement of blood pressure in the clinic during two study visits and outside of the clinic using ambulatory blood pressure monitoring and home blood pressure monitoring during sleep, a blood and urine sample, actigraphy and an echocardiogram. Height, weight and waist and neck circumference will be measured during a study visit by trained staff. Some participants may experience discomfort during the blood pressure measurements. However, the discomfort that is experienced is no more than that experienced during a routine outpatient doctor's visit. In our experience conducting ambulatory blood pressure monitoring on over 5,000 participants, none have experienced a serious injury. Participants will also complete questionnaires that ask about stress and psychosocial factors.

**Potential risks:** The physical risks of the studies are minimal, as no invasive procedures are proposed. Some discomfort may occur due to the use of the ambulatory blood pressure arm cuff or home blood pressure cuff, and no/minimal discomfort is expected with using the actigraph device (it is worn on the wrist like a watch). The discomfort, if it occurs, is minimal and temporary. Also, some patients may experience discomfort (i.e., dizziness) from the assessment of orthostatic hypotension. Patients may experience discomfort answering questions about stress and psychosocial risk factors. Study physicians will be available to discuss discomfort with patients and if necessary, participants will be referred to their doctor to discuss psychosocial factors. If the patient does not have a doctor, we will find a doctor for them to see. Data will be stored on encrypted computers at the field centers and at the University of Alabama at Birmingham (the coordinating center for this study). All data will be stored in locked filing cabinets to protect against the risk of a patient being identified. All findings will be presented in aggregate to ensure the confidentiality of all participants. After study completion, the clinic BP, ABPM and HBPM results will be given to the participants and invited to share it with their physician. If the participant does not have a physician, he/she will be referred to a physician for follow-up.

#### **E.1.2. Adequacy of Protection Against Risks**

**Recruitment and informed consent:** Participants for the proposed study will be enrolled following IRB-approved approaches. Potential participants for our study will be attending outpatient clinics affiliated with the University of Alabama at Birmingham or Columbia University. With IRB approval, potential participants will be contacted following a routine clinic by phone and screened for eligibility for the proposed study and, if eligible, will be told about the study, its goals, activities involved, and potential risks. Those who remain interested will be invited to participate. They will be provided with an informed consent for this study. The informed consent that will be used will be written at the sixth grade level and in a language that potential participants can understand. Individuals will be given time to read over the consent thoroughly and will be encouraged to ask questions to help them clarify any issues they might have. The principal investigators, co-investigators and staff at both sites (UAB and Columbia University) have substantial experience conducting research that includes explaining a study's purpose and potential risks and benefits to a broad range of participants.

**Protection against risks:** The physical risks of the studies are minimal, as no invasive procedures are proposed. Some discomfort may occur due to the use of the arm cuff for measuring blood pressure, and no/minimal discomfort is expected with using the actigraph device. The discomfort from the blood pressure cuffs, if it occurs, is temporary and should disappear when the cuffs are removed. Any discomfort, if it occurs, is minimal and temporary. The risks of having blood drawn include soreness and bruising at the puncture site, and sometimes there may be discomfort during the procedure. Occasionally participants feel lightheaded or faint. This may occur with the assessment of orthostatic hypotension as well. The assessment of orthostatic hypotension and the blood draw will occur in the presence of trained technicians with training handling safety issues for participants. A minimal risk to participants arises from the release of study data. To minimize this risk, staff conducting study visits will be trained in the protection of human subjects. In addition, all study information and the study computer will be kept in a locked room in at the participating field center and University of Alabama at Birmingham. The computer databases will be encrypted and protected by a

password available only to study investigators and other personnel who need access. The link between patient identity and a unique study identification number will be destroyed after the study is completed. Published reports will contain only aggregate and statistical results, and no individual results or patient identifiers will be disclosed. These safeguards make the possibility of a breach of confidentiality or invasion of privacy remote.

**Very high or low clinic BP.** Individuals with mean screening SBP of 110 to < 160 mm Hg and mean screening DBP of 70 to <100 mm Hg (based on the two most recent outpatient clinic visits, extracted from clinical records) will be included. Therefore, we are not including individuals with severely high or low clinic BP. Among enrolled participants, if clinic BP at any of the study visits  $\geq 160/100$  mmHg or <110/70 mmHg they will be referred to their health care provider for evaluation and excluded from the study for safety reasons.

